17.2 Subject Populations

The following populations will be used for the analysis of data for this study:

Per Protocol (PP) Population: All subjects who have been selected and received the specified drug at Visit 1 and do not have any important protocol deviations will be included in the PP population. The PP population will be the primary population for the analysis of efficacy.

Safety Population: All subjects who received the drug will be included in the safety population. The safety population will be the primary population for analysis of demographic, accountability, and safety measures.

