1. SYNOPSIS

Protocol No.: 16-043H

TITLE: Fibroblast Growth Factor Regeneration of Tympanic Membrane Perforations
INVESTIGATIONAL PRODUCT: Human fibroblast growth factor-2 (FGF-2/bFGF/FGF-II) in a gelatin sponge, adhered by fibrin glue
INDICATION: Treatment of chronic non-healing tympanic membrane perforation
PHASE OF DEVELOPMENT: Phase 2
INVESTIGATIONAL SITES/LOCATIONS: Mass Eye and Ear Infirmary, Boston, Massachusetts
STUDY DESIGN: A Phase II randomized trial will be initiated to evaluate efficacy as the primary measureable outcome. Eligible and consented patients will be randomized in a 3:1 ratio to the optimal biologic dose (OBD) of FGF-2 or placebo (sterile water) during the Randomized Treatment Phase. Application of the study treatment may occur at the initial Screening Visit (pending all eligibility requirements can be confirmed) or at Visit 1 and may be repeated at each follow up visit as needed for a maximum of three treatments in the Randomized Treatment Phase. These follow up visits will occur three weeks (+/- 7 days) from the last treatment application. During these visits, the subject's tympanic membrane will be examined, photographed, and additional otologic tests will be performed. If the perforation is found to be closed during these visits, then the subject will report in 2 months (+/- 7 days) for a final study visit. If the subject's TMP has not closed after the third and final application of their assigned treatment group, then the blind on the subject's randomization status will be broken, and placebo patients will be crossed over to receive unblinded study drug. Again, the subject may be given up to three additional treatments in the unblinded crossover phase. The follow up visits will follow the same schedule, occurring three weeks (+/- 7 days) from the last treatment. The same otologic procedures will be performed as in the previous visits. All subjects will report for a final study visit 2 months (+/- 7 days) after their last follow up visit when the perforation is determined to be closed or when the subject has completed the maximum number of study visits without perforation closure. The study will be completed for reporting purposes after all subjects have completed the 2 month (+/- 7 days) follow up final visit.
NUMBER OF SUBJECTS (PLANNED): 75

DIAGNOSIS AND MAIN CRITERIA FOR INCLUSION:

Key inclusion criteria:

- Age 18 years and older
- Dry tympanic membrane perforation of greater than 3 months duration

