14.1 Visit 0, Screening

The following procedures will be performed:

- Administration of Informed Consent Form
- Review of inclusion and exclusion criteria
- Medical history of the Tympanic Membrane
- Otologic Exam
- Vital Signs
- Laboratory evaluation (hematology and chemistry): *CBC, Basic Metabolic Panel Test, HbA1c*
- Pregnancy Test if applicable
- Review of Prior/ Concomitant medication(s)
- Optional: Study drug administration (if all eligibility requirements can be confirmed at this visit)
- Optional: TM photography
- Optional: Audiogram

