14.2 Visit 1, Day 1, IMP Administration

The following procedures will be performed:

- Review of inclusion and exclusion criteria
- Vital Signs
- Review of Prior/ Concomitant medication(s)
- TM photography- *if not done at the time of screening*
- Audiogram- *if not done at the time of screening*
- Study Drug Administration- *if not done at the time of screening*
- Assessment of Possible Adverse events

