17.1 Determination of Sample Size

The target enrollment of 60 subjects will provide sufficient power while also accounting for potential retention issues. With recruitment of only 44 subjects, we will reach a power of .80. This gives room for some attrition, although we think it will not be more than 5%.

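### The primary efficacy population requires drug at Visit 1, but the protocol allows the first application at screening (Visit 0)

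*Combined protocol and SAP*

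**What the plan says.** Section 17.2 (Subject Populations) defines the Per Protocol (PP) set as "All subjects who have been selected and received the specified drug at Visit 1 and do not have any important protocol deviations" and adds: "The PP population will be the primary population for the analysis of efficacy". The only other population defined there is the Safety population, which carries no visit condition. No intention-to-treat or full analysis set is defined.

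On the timing of the first dose, the synopsis states: "Application of the study treatment may occur at the initial Screening Visit (pending all eligibility requirements can be confirmed) or at Visit 1". Section 14.1 (Visit 0, Screening) lists "Optional: Study drug administration (if all eligibility requirements can be confirmed at this visit", and the schedule in 13.1 has a drug-administration mark in the Visit 0 column. Section 14.2 (Visit 1, Day 1) lists drug administration with the condition "if not done at the time of screening".

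Section 13.5 gives a second membership rule. To be evaluated for efficacy, a subject needs at least one treatment and a follow-up visit at 21 days (± 7 days). It does not say at which visit the treatment must be given.

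**The concern.** The PP entry condition names a visit at which some correctly treated subjects are not dosed. A subject who is randomised, treated at screening and fully compliant receives nothing at Visit 1 under 14.2, and so does not meet 17.2.

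Two outcomes are possible. If 17.2 is applied as written, these subjects leave the primary closure comparison for a scheduling reason, and the trial is small. If the analyst instead reads Visit 1 as the visit of first treatment, or applies 13.5, they stay in. The plan does not say which rule governs, so membership of the only defined efficacy population is not fixed before data are seen. Section 17.5 plans an interim analysis at about 30 subjects, so the question arises before the end of the trial.

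**Working it through.** **1. The rules applied to two compliant subjects**

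| Rule | First dose at Visit 0 | First dose at Visit 1 |
|---|---|---|
| Synopsis, 13.1, 14.1: first dose allowed at this visit? | Yes | Yes |
| 14.2: drug given at Visit 1? | No | Yes |
| 17.2: in the PP set? | No | Yes |
| 13.5: evaluable for efficacy, given a 21-day visit? | Yes | Yes |
| 17.2: in the Safety set? | Yes | Yes |

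The two subjects differ only in the calendar, yet 17.2 and 13.5 disagree about the first. No section states that Visit 1 means the first-dose visit wherever it falls, and 13.1 gives Visits 0 and 1 separate columns.

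One entry complicates this. In the 13.1 schedule the Visit 1 drug mark carries footnote 4, which makes treatment depend on the perforation still being open at that visit. Read literally, it could give drug at Visit 1 to a subject already dosed at Visit 0. Section 14.2 says otherwise.

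**2. Count needed to fall below the plan's own figure**

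Inputs: 44 subjects for power .80 (17.1: "With recruitment of only 44 subjects, we will reach a power of .80"); enrolment of 60 (synopsis statistical text, 17.1) or 75 (synopsis, 10.2). The documents disagree on enrolment, so both are shown.

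- N = 60: 60 − 44 = 16; 16/60 = 26.7%.
- N = 75: 75 − 44 = 31; 31/75 = 41.3%.

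More than 16 (or 31) subjects dosed at screening leaves fewer than 44, before any dropout. For N = 60, shares of 10%, 25% and 50% leave 54, 45 and 30 subjects. At 50% the placebo arm is 15 × 0.5 = 7.5, so 7 or 8 subjects.

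**3. What that does to power**

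The stated power cannot be reproduced strictly, because the plan gives no design closure rates. The following is illustrative: two-sided Fisher's exact test at 0.05, power by exact enumeration over both binomials. I assumed placebo closure of 10% to 40% and solved for the FGF-2 rate that gives 80% at 33:11 (44 subjects, 3:1). The arms are reduced by the assumed Visit 0 share and rounded.

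| Placebo / FGF-2 closure | 45:15 (0%) | 34:11 (25%) | 22:8 (50%) | 11:4 (75%) |
|---|---|---|---|---|
| 10% / 55.4% | 91.5% | 77.8% | 57.2% | 13.4% |
| 20% / 69.3% | 91.3% | 82.5% | 68.0% | 26.8% |
| 30% / 79.2% | 91.6% | 82.4% | 67.9% | 32.0% |
| 40% / 86.3% | 91.0% | 83.3% | 66.0% | 31.0% |
| 10% / 98.1% (cited study, 3.2) | about 100% | about 100% | about 100% | 94.3% |

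Under the calibrated rates, 45:15 gives 91.0% to 91.6%, so the synopsis's claim of more than 90% and 17.1's .80 at 44 agree with each other. After the 5% dropout (60 × 0.95 = 57, taken as 43:14) the range is 86.9% to 91.5%. The cited-study rates give about 100% at 33:11, so they cannot be the rates behind .80 at 44.

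For N = 75 (56:19) the calibrated rates give 96.0% to 96.8% with no loss, 88.1% to 89.1% at a 25% share (42:14), 64.4% to 77.5% at 50% (28:10) and 35.1% to 46.3% at 75% (14:5).

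**The case against.** The best reply is that Visit 1 is only a label for the first-treatment visit. Section 14.2 couples Visit 1 with Day 1 and administration of the product; 14.4 to 14.7 count days from the first treatment; 5.1 treats Visits 1 to 3 as the treatment visits. The wording may well be a leftover from before same-day dosing was allowed. Section 13.5 also supplies a written rule that includes these subjects, so it would be too strong to infer that keeping them has no basis in the plan. This explains the wording but does not settle it: 14.2 keeps Visit 1 distinct from a screening dose, and 17.2, not 13.5, is what defines the primary population.

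Other stronger readings are tempting and go beyond the documents:

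- **That every subject dosed at screening is excluded.** Footnote 4 in 13.1 leaves open a dose at Visit 1 for some of them, in conflict with 14.2.
- **That the comparison is biased or the remaining set distorted.** Whether eligibility is confirmed the same day is settled before treatment, and the pharmacy holds the assignments under blinding (section 6), so exclusion should not differ by arm. Nothing in the documents shows that subjects dosed at screening have a different prognosis for closure.
- **That power falls below .80 at 27%.** This uses 60 only; with 75 the count is reached at 41%. In both cases the power itself rests on unstated closure rates.

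**Conclusion.** The definition is wrong as written. Section 17.2 read literally drops compliant subjects whose first application was at screening, and it conflicts with 13.5. That conclusion rests on the text alone.

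The numerical size is conditional. It depends on the share dosed at Visit 0, on whether enrolment is 60 or 75, and on closure rates, of which the first and third are not stated and the second is stated inconsistently. Under the calibrated rates with 60 enrolled, a 25% share brings power to about 78% to 83% and a 50% share to about 57% to 68%. Under the cited-study rates there is practically no loss up to a 50% share. The certain harm is a primary set that is not fixed in advance, together with some loss of numbers if 17.2 is followed literally.

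**What to change.** Before any interim look or unblinding:

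1. In 17.2, replace the Visit 1 condition with receipt of at least one application of the assigned treatment (FGF-2 or placebo), at Visit 0 or Visit 1.
2. Align 17.2 with 13.5 so that one efficacy-membership rule applies. State whether the 21-day visit is a condition of membership, and make this consistent with the synopsis rule that counts discontinued subjects as not improved.
3. Reconcile footnote 4 on the Visit 1 drug mark in 13.1 with 14.2. Which of the two is correct is for the sponsor and investigators to settle.

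The cost is a sentence or two in 17.2 and 13.5 and one clarified footnote, with no extra subjects or data. With item 1 in place, no subject is lost for having been dosed at screening.

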- 3) Place a human fibroblast growth factor-2 (FGF-2) soaked pledget of bioabsorbable gelatin sponge larger than the tympanic membrane so the tympanic membrane is completely covered.
- 4) Secure the pledget in place with several drops of fibrin glue.
- 5) After the effects of the topical anesthetic have worn off, if any, the patient is released with the following instructions:
 - a) Avoid violently sniffling or blowing the nose
 - b) Sneeze and cough naturally through the mouth without occluding the mouth with the hand.
 - c) Use cotton balls covered with petroleum jelly on the outer surface when washing the hair and bathing. This is needed to help keep water out of the ear.
 - d) Avoid using a hearing aid in the treated ear.
 - e) Avoid flying, using elevators in tall buildings, and other situations involving substantial changes in air pressure.
 - f) Avoid swimming.

DISCONTINUATION FROM TREATMENT:

Reasons for permanent discontinuation include the following:

If the first treatment does not result in complete closure, subsequent treatments will not be administered if any ear complications occur in the treated ear, including but not limited to infection, moderate to severe pain, moderate to severe irritation, or clinically significant sensorineural hearing loss. All subjects will complete all safety follow up visits.

PRIMARY ENDPOINT:

The tympanic membrane and surrounding structures will be examined every 21-days (+7 days) for up to three visits. Adverse events will be recorded at all visits. Routine laboratory tests will be performed at the screening visit and at the final study visit. Vital signs will be assessed at each study visit and changes in clinical examination findings will be noted.

SECONDARY ENDPOINTS:

- Tympanic membrane perforation closure determined by otoscopic exam and photographic documentation
- Pure-tone and speech discrimination scores as measured by pre- and post-treatment audiograms
- Mobility of the tympanic membrane as measured by tympanometry
- Salvage rate of FGF-2 in patients who fail placebo

STATISTICAL ANALYSIS:

The target enrollment of 75 subjects will provide sufficient power while also accounting for potential retention issues. The primary endpoint is to confirm the efficacy of

FGF-2 in subject with TMR by testing the hypothesis that the rate of subject with complete closure of the TMR will be superior to that placebo.

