The sample size is calculated in 3:1 ratio to FGF-2 treatment group or placebo to provide more than 90% power to detect a clinical significant difference at a two-sided significance level of 0.05 using a Fisher's exact test. To allow for 5% dropouts, 45 patients of FGF-2 treatment group and 15 patients of placebo are required.

Data after discontinuations for any reason will not be imputed through the final schedule visit. This subject will be considered as not-improvement.

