Once the subject completes Visit 1, Visit 2, and Visit 3, the subject will come back for Visit 4 (+/- 7 days). During this visit, the perforation will be examined again. If the perforation has not closed completely at this visit, then the blind on the subject's randomization status will be broken. If the subject was randomized to placebo, s/he will be crossed over to receive unblinded FGG-2 treatment. If the subject was randomized to FGF-2 treatment, s/he will receive no further study treatment and return in two months (+/- 7 days) for the final follow up visit.

If crossed-over to unblinded FGF-2 treatment, the subject may be given up to three additional treatments. The follow up visits will occur three weeks (+/- 7 days) and the same otologic procedures will be conducted as mentioned before (See Section 13.1, Schedule of Assessments). If the perforation is found to be closed during these visits or when the subject has completed the maximum number of study visits without perforation closure, then the subject will report in 2 months (+/- 7 days) for a final visit. The study will be completed for reporting purposes after all subjects have completed the 2 month (+/- 7 days) follow up final visit.

6. Discussion of Study Design

The investigator and the subject will be blinded to treatment assignment during the Randomized Treatment phase. Subjects whose perforations fail to close during the randomized treatment phase will crossover to the Unblinded Crossover Phase. During the crossover phase, only those subjects who failed placebo will receive unblinded FGF-2 treatment. The rationale for using a dose of 20 μ g in 0.2ml is based on the maximum effective dosages as reported in humans of TMR closure with FGF-2 (Kanemaru et al., 2011).

The subjects, physician, and other study staff members will remain blinded to the treatment arm during the randomized treatment phase as the pharmacy will oversee the randomization process. During the Randomized Treatment phase, the pharmacy will provide the appropriately blinded vial of either FGF-2 or placebo solution as needed upon the request from the physician. Only those subjects who fail the randomized treatment phase will crossover into the unblinded crossover phase. Documentation of the cross-over will be made in the Case Report Forms as well as in the randomization log managed centrally by the dispensing pharmacy.

7. Selection of Study Population

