13.5 Treatment Requirements

Subjects must complete at least 1 treatment and have a follow up visit at 21 days (± 7 days) to be evaluated for efficacy.

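### Section 17.2 makes a per-protocol set primary for a superiority hypothesis, defines no all-randomised set, and leaves early losses and the timing of exclusions unsettled

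*Combined protocol and SAP*

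**What the plan says.** The Synopsis (Statistical Analysis) sets the aim as showing that "the rate of subject with complete closure of the TMR will be superior to that placebo". It sizes the trial "to provide more than 90% power to detect a clinical significant difference at a two-sided significance level of 0.05", by Fisher's exact test, and says that "45 patients of FGF-2 treatment group and 15 patients of placebo are required" with 5% dropout allowed for.

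Section 17.2 defines two sets only. The safety set is everyone who received the drug. The per-protocol (PP) set is those who were selected, "received the specified drug at Visit 1 and do not have any important protocol deviations". Of the two, "The PP population will be the primary population for the analysis of efficacy". No intention-to-treat, full-analysis or all-randomised set appears anywhere in the document.

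Two other places bear on a subject who is dosed and then lost early:
- Section 13.5, as a condition for efficacy evaluation: "Subjects must complete at least 1 treatment and have a follow up visit at 21 days" (±7 days).
- Synopsis: "Data after discontinuations for any reason will not be imputed through the final schedule visit. This subject will be considered as not-improvement".

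On unblinding, Section 5.1 says of Visit 4: "If the perforation has not closed completely at this visit, then the blind on the subject's randomization status will be broken". Section 14.4 repeats this.

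**The concern.** A superiority comparison is normally protected by analysing everyone randomised in the arm assigned. Here the primary set can lose subjects after randomisation, on a criterion that the plan does not define.

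Two things follow.

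1. **Timing of exclusions.** At Visit 4, arm becomes known for exactly the subjects who have not closed. If their deviations are judged after that, they can be judged with both arm and outcome known. The plan neither schedules this nor prevents it. One possible route (an inference, not something the plan describes): Section 12.1 prohibits certain ear drops because they may interfere with efficacy evaluation, and the Synopsis and Section 7.3 list ear infection among the reasons for giving no further treatment. A subject given such drops for an infection could be classed as a deviation and excluded, or as a discontinuation and counted as not improved.

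2. **Denominator.** A subject dosed but not seen at 21 days leaves the analysis under one reading of Section 13.5 and is a failure under the Synopsis. Two statisticians following the plan could report different primary results.

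**Working it through.** **1. The plan's own figure.** No closure rates are given for the sample size, so 45:15 cannot be derived forward. It can be checked for consistency. Section 17.1 claims power of .80 with 44 subjects (33:11 at 3:1). Solving for the FGF-2 rate that gives 80% Fisher power at 33:11, then computing power at 45:15:

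| Assumed placebo rate | FGF-2 rate solved | Power at 45:15 |
|---|---|---|
| 10% | 55.4% | 0.915 |
| 20% | 69.3% | 0.913 |
| 30% | 79.2% | 0.916 |

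The two power statements therefore agree with each other. The one human gelatin-sponge and fibrin-glue study with controls described in Section 3.2 (98.1% vs 10%) gives power of about 1.00 at both sizes, so it is not the source of the .80.

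**2. Inputs for the early-loss check.**
- 45:15 and two-sided Fisher p < 0.05 (Synopsis). Section 17.5 names other tests and says alpha is not conserved at 0.05, so this decision rule is itself an assumption.
- Losses: 5% of 60 = 3 (Synopsis, Section 17.1).
- Assumed closure rates among subjects seen: 55/10, 69/20, 75/25 and 79/30 (%). Power with no loss is 0.910, 0.909, 0.918 and 0.913.

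**3. How the losses fall.** If loss is independent of arm, P(a in FGF-2, b in placebo) = C(45,a)·C(15,b)/C(60,3), with C(60,3) = 34,220:
- 3:0 → 14,190/34,220 = 0.415
- 2:1 → 14,850/34,220 = 0.434
- 1:2 → 4,725/34,220 = 0.138
- 0:3 → 455/34,220 = 0.013

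**4. Probability that the two rules differ on significance.** Exact enumeration over all outcomes: losses excluded versus losses counted as not closed.

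| Rates | 3:0 | 2:1 | 1:2 | 0:3 | Weighted | Exclusion gains / loses significance |
|---|---|---|---|---|---|---|
| 55/10 | 0.0383 | 0.0317 | 0.0749 | 0.0934 | 0.0412 | 0.0159 / 0.0253 |
| 69/20 | 0.0635 | 0.0072 | 0.0764 | 0.0946 | 0.0413 | 0.0280 / 0.0133 |
| 75/25 | 0.0703 | 0.0141 | 0.0578 | 0.0933 | 0.0445 | 0.0350 / 0.0095 |
| 79/30 | 0.0871 | 0.0248 | 0.0542 | 0.1086 | 0.0558 | 0.0460 / 0.0098 |

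First row: 0.415×0.0383 + 0.434×0.0317 + 0.138×0.0749 + 0.013×0.0934 = 0.041.

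At 75 subjects (the Synopsis planned number; 56:19, with 5% of 75 = 3.75, taken as 4 losses) the weighted figures are 0.0176, 0.0196, 0.0244 and 0.0318. At 98.1/10 they are 0.0000 at either size.

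**5. Excluding non-closers in one arm.** This bears on PP versus all-randomised itself. Suppose both arms truly close at rate q and a share f of FGF-2 non-closers is excluded. The apparent FGF-2 rate is q/[q + (1−q)(1−f)]. With f = 10%:
- q = 0.3: 0.3/0.93 = 0.3226, bias +2.3 points; one-sided rejection 1.77% → 2.15%
- q = 0.4: 0.4/0.94 = 0.4255, bias +2.6 points; 1.77% → 2.29%
- q = 0.5: 0.5/0.95 = 0.5263, bias +2.6 points; 1.67% → 2.57%

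These remain at about the nominal 2.5%. At f = 20% (0.2×45×(1−q) = 4.5 to 6.3 subjects) rejection reaches 3.1–3.9%. Equal exclusion in both arms gives no bias; exclusion in placebo only gives −2.3 to −2.6 points.

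**The case against.** The case for leaving the plan alone, or for asking only for clarification, has real force.

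- **The early-loss passages may be compatible.** Section 13.5 could define who is evaluable, and the Synopsis could say how an evaluable subject who later discontinues is scored. A reader might infer a flat contradiction; the text does not establish one. But the reconciling reading is not written down, and Section 17.2 is where it belongs.
- **Unblinded classification is inferred from silence.** A reader might conclude that deviations will be judged after unblinding. No section says so. What stands is narrower: nothing rules it out.
- **Exclusions would be visible.** Section 17.3 reports population counts by treatment, reasons for early termination and listings for all subjects. That exposes unequal exclusion afterwards, but it neither prevents it nor supplies an all-randomised result for comparison.
- **The PP set is not narrow.** It does not demand completed treatment or follow-up; it departs from all-treated only through important deviations.
- **The figures mostly measure the early-loss rule**, not PP against all-randomised, and they presuppose a 0.05 Fisher decision that Section 17.5 leaves open. Both points are right. The largest entries, 9.3–10.9%, need all three losses in placebo, which has weight 0.013.

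**Conclusion.** The point holds as a should-fix matter. The primary efficacy population for a superiority hypothesis is a PP set with an undefined exclusion criterion, no all-randomised set is defined, no safeguard on timing is stated, and two early-loss rules are not reconciled.

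The expected size is modest: the early-loss choice alters significance in 4.1–5.6% of trials at 45:15 and 1.8–3.2% at 56:19, in either direction, and never at 98.1% versus 10%. This rests on assumed closure rates, losses of about 5% independent of arm, and a two-sided Fisher test at 0.05.

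A reader might infer that the PP choice inflates the false-positive rate or systematically favours FGF-2. The documents do not support that. Excluding 10% of FGF-2 non-closers leaves the error rate about nominal, the 20% pattern is suggested nowhere in the plan, and at 55% versus 10% dropping early losses costs significance more often than it gains it. The case for change is that the primary population should be fixed in advance, not that a large bias is expected.

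**What to change.** 1. Make all randomised subjects, analysed by assigned arm, the primary efficacy population.
2. Use observed closure status at the subject's last randomised-phase assessment, up to Visit 4 and before any crossover FGF-2, including after treatment is stopped. Follow-up continues (Synopsis, Section 7.3) and photographs are taken at every visit (Section 13.2). Count a subject as not closed only if that status is missing, and amend the Synopsis sentence to match.
3. State how the Section 13.2 durability requirement applies. It refers to a test-of-cure Visit 5, but Section 14.5 describes Visit 5 as a visit for crossed-over subjects. Say how a subject who closed in the randomised phase and misses the later visit is scored.
4. Keep PP as supportive and limit Section 13.5 to it.
5. List important deviations in advance. Classify them before each subject's Visit 4 unblinding, or by staff blind to arm and closure.
6. Add a sensitivity analysis: missing excluded; and missing FGF-2 not closed with missing placebo closed.

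**Cost.** Wording and one table, with no extra visits or subjects. Closure rates become slightly lower. With 3 losses independent of arm, power is 87–88% against 88–91% under exclusion, ranging from a gain of 0.9 points at 55/10 to a loss of 3.6 points at 79/30. Counting missing as not closed is not uniformly conservative: with all 3 losses in FGF-2, power is 82–86% against 90–91% under exclusion; with all 3 in placebo it is 95–97% against 85–88%. Hence item 6.
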